6.3.3 Screening

Screening for eligible patients will be done entirely by the algorithm built into our best practice alert within the Epic electronic medical record. This algorithm will identify any hospitalized patients at all participating hospitals who have AKI (based on KDIGO creatinine criteria). Upon opening of a patient chart, the algorithm will examine the most recent creatinine value against the minimum value in the past 48 hours and 7 days. If the current value is 0.3 mg/dl above the 48 hour minimum, or 50% higher than the 7 day minimum, the patient meets AKI criteria. If the patient meets all other inclusion and exclusion criteria, the patient will be automatically enrolled into our study and randomized into the “recommended” or “anti-recommended” group. Whether or not a subject generates an alert in either study arm will depend on the uplift score generated for each subject by the uplift algorithm. Those whose uplift score represents a probability of benefit greater than 0.5 will generate an alert in the “recommended” study arm, but will not generate an alert in the “anti-recommended” study arm. Those whose uplift score represents a probability of benefit less than 0.5 will not generate an alert in the “recommended” study arm and will generate an alert in the “anti-recommended” study arm.

6.3.4 Enrollment

Patients are automatically and immediately enrolled into our study if our best practice alert confirms their eligibility as described above.

6.3.5 On Study Visits

N/A

6.3.6 End of Study and Follow-up

There will be no patient follow-up and patients will not be able to withdraw from the study. We do not plan to inform subjects of their participation in the trial. We feel that the results of this study will not be pertinent to the subjects, as the effect of the alert is expected to be transient and should have no impact on their future quality of life beyond that measured by the outcome of the study itself. Moreover, post-hoc disclosure of the nature of the study to

the subjects may generate undue stress and concern on the part of the subject as to the quality of their overall clinical care.

We will update all clinicians of the results of this trial after trial completion. We are not collecting data that would tie a specific clinician to an outcome. For example, while we would inform clinicians that the alerts increased or decreased the rate of certain outcomes, we will not be able to tell them what their specific rate of use of best practices are or their individual impact on outcomes.

6.3.7 Removal of subjects

N/A

6.4 Statistical Method

6.4.1 Statistical Design

The primary analysis will utilize the intention to treat principle. The primary outcome (a composite of progression of AKI, dialysis, and death) will be compared across the groups using the Mantel-Haenszel chi-square test to account for the 4 randomization strata (which account for the four enrolling hospitals in the study). Final statistical significance will be based on a p-value of <0.044 to account for the interim analysis.

In addition, it is possible that the alert may change clinician behavior over time such that best practices are performed at a higher rate even in the absence of the alert. A retrospective examination will be performed to assess improvement in the control group before / after intervention as a measurement of contamination. We expect that providers who receive AKI alerts on some patients may be more likely to look for AKI in other patients, potentially diluting the effect of the intervention – this pre/post intervention analysis will help in assessing that level of contamination.

We have specified several subgroups in whom the benefit of an AKI alert may differ from the general population. These groups will be analyzed as secondary and exploratory analyses. They include:

- Surgical patients
- Subjects with baseline creatinine <1.0mg/dl
- Subjects with baseline creatinine <0.5 mg/dl
- Female participants (due to lower rate of increase in creatinine after AKI)
- Black participants (due to higher rate of increase in creatinine after AKI)
- Elderly subjects (age > 65, age > 70, and age > 75)
- Subjects in an ICU at the time of the alert
- Subjects who enter the study based on relative vs. absolute creatinine criteria vs. both

Finally, as the academic year progresses, new clinicians (such as residents and interns) may become more facile in their ability to recognize AKI, which may attenuate the effect of this intervention. We will model this in exploratory analyses using an intervention-by-time of year interaction term in models of the primary outcome.

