50 features were selected to be included in the policy. The 10 top features selected to be most predictive of alert benefit/harm are:

- 1) Most recent diastolic blood pressure
- 2) Most recent systolic blood pressure
- 3) Prior receipt of ultrasound for deep venous thrombosis within the current encounter
- 4) Prior receipt of a transthoracic echocardiogram within the current encounter
- 5) Prior exposure to insulin within the current encounter
- 6) Prior exposure to docusate within the current encounter
- 7) Prior exposure to miralax within the current encounter
- 8) Whether opiates were detected in the urine within the current encounter (binary variable; 1 = yes; 2 = no)
- 9) Whether the patient had their blood type tested with an ‘A’ result (binary variable; 1 = yes; 2 = no)
- 10) Whether the patient had a thyroid-stimulating hormone measurement within the current encounter (binary variable; 1 = yes; 2 = no)

Various alternative models were fit in the training set; however, the described model had the best c-statistic in the validation set.

In the current study, all hospitalized patients with AKI will be automatically enrolled and randomized into our trial. Prospectively, the deterministic policy will be applied to each enrolled patient; when combined with a randomization step, this will determine alert vs usual care. We further detail this randomized process below. For those randomized to follow our policy, we expect 51% of the total AKI population within our study sites to be sent alerts.

Subject Eligibility

Identification of patient subjects will be performed entirely within the Epic electronic medical record system based on inclusion and exclusion criteria outlined below. Eligible patients will be identified by our algorithm embedded into our best practice alert with the Epic electronic medical record. This algorithm will identify any hospitalized patients at all participating hospitals who have AKI (based on KDIGO creatinine criteria). To do this, upon opening of a patient chart, the algorithm will examine the most recent creatinine value against the

minimum value in the past 48 hours and 7 days. If the current value is 0.3 mg/dl above the 48 hour minimum, or 50% higher than the 7 day minimum, the patient meets AKI criteria.

Randomization

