 - Phosphorus (BH GH L LMW YH): Once For 1 Occurrences
- Diagnostic Orders:**
 - US, RETROPERITNL ABD, LTD: STAT
 - Bladder scan: STAT, FOUR TIME A DAY SCHEDULED When?
- Nursing Orders:**
 - Intake and output: Routine, EVERY 8 HOURS SCHEDULED
 - Measure weight: Routine, DAILY SCHEDULED
- Dietary Orders:**
 - Diet Renal Non Dialysis: DIET EFFECTIVE NOW, Starting today
Safety Tray? (Suicide/Homicide/Police Custody):
Total calories:
Fat Restriction:
Protein restriction:
Sodium Restriction: 2 gm NA
Potassium Restriction: 2gm k
Phosphorus restriction: 1000 mg phos
Fluid Restriction:
Additional Restrictions:
Diet Considerations:
Texture:
Initiate Nutrition Management Protocol (Yes/No?): Yes - Initiate Protocol

Non-alert

Patients who are not selected to receive the alert will not generate an alert in the medical record, and will continue to receive standard of care.

Study Timeline

We plan to activate our targeted alert in a step-wise fashion throughout our 4 study hospitals, beginning in Yale New Haven Hospital, followed by St. Raphael's Campus, Bridgeport Hospital and Greenwich Hospital.

Staggered enrollment will allow for proper pre-trial education as well as adequate site visits, study monitoring, quality control and clinician engagement at each site as roll out begins.

Study Outcomes

Our primary outcome will be a composite of AKI progression, dialysis (hemodialysis, continuous renal replacement therapy, or peritoneal dialysis), or mortality within 14 days of randomization.

Secondary study endpoints will look at a variety of patient outcomes as well as best practice metrics, including the following:

- Inpatient mortality
- 14-day mortality
- Inpatient dialysis
- 14-day dialysis
- Discharged on dialysis
- Percent who progress to stage 2 AKI
- Percent who progress to stage 3 AKI
- AKI duration
- 30-day readmission rate
- Cost of index hospitalization
- AKI documentation
- “Best practice” outcomes: Proportion achieved per patient during index hospitalization:
 - Contrast administration
 - Fluid administration
 - Aminoglycoside administration
 - NSAID administration/cessation
 - ACEi administration/cessation
 - Urinalysis order
 - Documentation of AKI
 - Monitoring of creatinine
 - Monitoring of urine output
 - Renal consults

All investigators will be blinded to the treatment assignment until the end of the trial period.

Clinician Outreach and Engagement

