6.5.3 Exploratory Objectives Analyses (if applicable)

A retrospective examination will be performed to assess improvement in the control group before / after intervention as a measurement of contamination. We expect that providers who receive AKI alerts on some patients may be more likely to look for AKI in other patients, potentially diluting the effect of the intervention – this pre/post intervention analysis will help in assessing that level of contamination.

We have specified several subgroups in whom the benefit of an AKI alert may differ from the general population. These groups will be analyzed as secondary and exploratory analyses. They include:

- Surgical patients
- Subjects with baseline creatinine <1.0mg/dl
- Subjects with baseline creatinine <0.5 mg/dl
- Females (due to lower rate of increase in creatinine after AKI)
- African Americans (due to higher rate of increase in creatinine after AKI)
- Elderly subjects (age > 65, age > 70, and age > 75)
- Subjects in an ICU at the time of the alert
- Subjects who enter the study based on relative vs. absolute creatinine criteria vs. both

Finally, as the academic year progresses, new clinicians (such as residents and interns) may become more facile in their ability to recognize AKI, which may attenuate the effect of this intervention. We will model this in exploratory analyses using an intervention-by-time of year interaction term in models of the primary outcome.

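### The contamination check is an uncontrolled before/after change in a 'control group' that this design does not define, so calendar drift and clinician education cannot be separated from contamination

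*Combined protocol and SAP*

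**What the plan says.** Section 6.4.1 raises the possibility that the alert changes clinicians' habits so that "best practices are performed at a higher rate even in the absence of the alert". It then states the check: "A retrospective examination will be performed to assess improvement in the control group before / after intervention as a measurement of contamination". Section 6.5.3 repeats the plan among the exploratory analyses and concludes that "this pre/post intervention analysis will help in assessing that level of contamination". Neither section names the pre-period, the outcome to be compared, a time adjustment or a concurrent reference.

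The randomised contrast is as recommended versus anti-recommended. Under section 6.3.3, patients with a score below 0.5 "will not generate an alert in the “recommended” study arm and will generate an alert in the “anti-recommended” study arm"; patients above 0.5 are handled the other way round. Section 5.1 gives the expected split: "For those randomized to follow our policy, we expect 51% of the total AKI population within our study sites to be sent alerts".

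Two other parts of the plan bear on timing. Section 6.4.1 expects that "as the academic year progresses, new clinicians (such as residents and interns) may become more facile in their ability to recognize AKI", and handles this with an interaction term in models of the primary outcome. Section 5.1 (Study Timeline) says "We plan to activate our targeted alert in a step-wise fashion throughout our 4 study hospitals", but does not link the roll-out to the contamination check.

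**The concern.** A before/after look at the control group suits a trial with an unalerted control arm. Here neither arm is unalerted, so the analyst must decide what the term means, and the documents use it in two ways:

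- **As one side of the randomised comparison.** The first paragraph of section 6.5.1 pairs it with the intervention group when describing the primary analysis.
- **As patients without an alert.** The second paragraph of 6.5.1 contrasts alert with control. Section 3.2.1 attaches overtreatment to the intervention group and undertreatment to the control group, which makes sense only if control means no alert.

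Whichever is meant, nothing in the comparison stands for what would have happened over the same period without the trial. Besides the learning that the plan expects, section 5.1 (Clinician Outreach and Engagement) and section 6.5.4 describe clinician education before activation and periodically afterwards. All of this would be counted as contamination.

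What is at stake is interpretation. Contamination is the stated reason for raising the sample size by 20% (section 6.4.2), and this is the only planned check on it. Section 6.5.4 says that finding no effect would lead to advice against continuing AKI alerts, so readers of a null result will ask how much of it is dilution.

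**Working it through.** **The plan's own figures.** Section 6.4.2: 3,410 × 1.2 = 4,092, as stated. For scale, a 20% increase offsets a dilution of the treatment difference of about 1 − √(1/1.2) = 8.7%. The documents give no estimate of contamination with which to compare this.

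**Alerted share by arm.** With 51% alerted in the recommended arm (section 5.1), the anti-recommended arm has 1 − 0.51 = 49% alerted. At 1:1 allocation the overall share is 0.5 × 0.51 + 0.5 × 0.49 = 50%, which agrees with section 5.1 (Randomization). The ratio is not stated. However, alert status can be random with respect to score, as that section says, only if allocation is 1:1.

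**Who the unalerted patients are.** At 1:1, with 2,046 patients per arm:

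- from the anti-recommended arm, score above 0.5: 0.51 × 2,046 ≈ 1,043
- from the recommended arm, score below 0.5: 0.49 × 2,046 ≈ 1,003
- high-score share of the pool: 1,043 / 2,046 ≈ 51%, the same as in the whole AKI population

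Pooled over both arms, unalerted patients are a random half of those enrolled. Taken from the anti-recommended arm alone, they all have scores above 0.5 and would need a score-matched pre-period group.

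**What the before/after change measures.** Let a be the alerted share of the chosen group, D the direct effect of an alert on a best-practice rate, S the true spillover to unalerted patients, and T the change over calendar time from other causes, including education. Then

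apparent contamination = a·D + (1 − a)·S + T.

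D, S and T are not in the documents. I assume D of 5 to 10 points, S of 0 to 3 and T of −3 to +3.

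| Group used | S | T | Apparent contamination (points) |
|---|---|---|---|
| Anti-recommended arm, a = 0.49 | 0 | 0 | 0.49 × 5 = 2.45 to 0.49 × 10 = 4.9 |
| Anti-recommended arm, a = 0.49 | 0 | −3 to +3 | 2.45 − 3 = −0.55 to 4.9 + 3 = 7.9 |
| Unalerted patients, a = 0 | 0 | −3 to +3 | −3 to +3 |
| Unalerted patients, a = 0 | 3 | −3 | 0 |

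For unalerted patients the alert-effect term is zero, but drift still enters one for one. It can create apparent contamination where there is none (third row) or hide it where it exists (fourth row).

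**The case against.** The best case for the plan is that the context settles the meaning. The sentence before the check concerns care given without an alert, and the sentence after it concerns providers looking for AKI in other patients. Sections 3.2.1 and 6.5.1 (second paragraph) agree. On that reading the 49% is irrelevant. The learning that the plan expects is seasonal and enrolment is planned for one year (section 5.1.1), so a pre-period of matching months would largely cancel it. The analysis is exploratory, and no stopping rule or sample-size rule uses it.

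Most of this stands. A reader might infer that the check will certainly be run on an arm that is half alerted; the documents do not support that, and only the general phrase in the first paragraph of 6.5.1 points that way. A reader might also infer that unalerted patients are a score-selected group. Under 1:1 allocation and pooling over both arms they are not, as shown above. Nor can one state how large the artefact is relative to true contamination, because the documents give no spillover rate; the 20% in section 6.4.2 is a sample-size increase.

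What remains is that the plan does not write down the favoured reading and does not specify matching months. Matching months would also leave year-on-year trend and education in the estimate.

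**Conclusion.** The point holds in a limited form. The group is undefined for this design, although context favours unalerted patients, and the comparison is uncontrolled under either reading. If the anti-recommended arm were used, 49% of the direct alert effect would be counted as contamination: 2.5 to 4.9 points on the assumed 5 to 10 point effect. If unalerted patients are used, that error vanishes, but calendar drift and education still enter in full, in either direction.

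The bias is possible, not certain; its size depends on drift that the documents do not quantify. It would be going too far to conclude that a null primary result will be wrongly explained. The check is exploratory and the randomised primary comparison is unaffected. This is a cheap improvement of low priority.

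**What to change.** In sections 6.4.1 and 6.5.3:

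1. **Define the group.** Replace the control group with patients who generated no alert, pooled over both arms, and state the allocation ratio. Stratifying by score is then optional. It is needed only if a single arm is used, and the score must then be calculated retrospectively for pre-period patients.
2. **Control the comparison.** Compare these patients with AKI patients who met the same eligibility criteria at the same hospital before activation, in matching calendar months, using a model with hospital and calendar-trend terms. State a pre-period long enough to support the trend term, and name the outcome; the per-patient proportion of best practices in section 5.2.2 is already defined.
3. **Add a supporting reference.** During the stepwise roll-out, use hospitals not yet activated as a concurrent reference.

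The cost is SAP wording and analysis time; any before/after analysis already needs an extract of pre-activation patients. Randomisation, sample size and the primary test do not change.

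The staggered reference cannot stand alone. Step lengths are not given, precision will be poor if the steps are short, and there is no concurrent reference once the fourth hospital is active. The sites share one health system, so spillover or early education at a site not yet active would bias that reference toward no contamination. Education delivered close to a site's activation will stay partly mixed with contamination, and the report should say so.

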6.4.2 Sample Size Considerations

Based on analysis of the ELAIA-1 trial (restricted to the sites planned for ELAIA-3) we estimate that the overall outcome rate in the “anti-recommended” arm will be 24%, and the rate in the “recommended” arm will be 20% lower, 19.2% . At a total alpha threshold of 0.05, we will have 90% power to detect a difference of at least this great or greater by enrolling 3,410 individuals. We are increasing this target sample size by 20% to 4,092 to account for contamination across the study arms.

6.5 Planned Analyses

6.5.1 Primary Objective Analysis

For the primary analysis, and all comparisons of categorical variables between the intervention and control group, we will use the Mantel-Haenszel test, accounting for each hospital site as an individual stratum. The Mantel-Haenszel approach will be used to obtain the pooled relative risks across hospital strata without adjusting for other baseline factors.

The primary analysis will examine the rate of the primary outcome in groups defined by whether the individual was randomized to “as recommended” vs. “anti-recommended”. The effect of alert vs control (which is also randomized in this framework) will be considered a secondary outcome.

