5.2 Outcome Variables

5.2.1 Primary Outcome Variables

The primary outcome will be a composite of AKI progression, inpatient dialysis, and inpatient death within 14 days of randomization.

Progression of AKI is defined as the increase in KDIGO stage from the time of randomization to the present. For patients who are discharged, we will impute 14-day creatinine using the last observation carried forward method.

Dialysis is defined as the receipt of hemodialysis, continuous renal replacement therapy, or peritoneal dialysis. Isolated ultrafiltration treatments will not be included.

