6.5.6 Interim Analysis (if applicable)

We plan to do three interim analyses, and guidelines will be given to the DSMB for stopping the trial for efficacy, harm, and futility. Our interim analyses will be conducted as follows:

The interim analyses will be performed at 25%, 50%, and 75% enrollment. At the first interim analysis, the trial will stop for efficacy if the p-value is < .0016. At the second interim analysis, the trial will stop for efficacy or futility if the p-value is < .0048 or > .72 and < .014 and > .22 for the third interim analysis. The p-value threshold for the final analysis of the primary outcome is set at <0.044.

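### The primary analysis adjusts for hospital only and excludes prognostic baseline data already in the record, giving up precision that would cost nothing to collect

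*Combined protocol and SAP*

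**What the plan says.** Section 6.4.1 compares the primary composite between arms "using the Mantel-Haenszel chi-square test to account for the 4 randomization strata", the strata being the four hospitals. Section 6.5.1 adds: "The Mantel-Haenszel approach will be used to obtain the pooled relative risks across hospital strata without adjusting for other baseline factors". The only other models of the primary outcome are exploratory ones with an intervention-by-time-of-year interaction (sections 6.4.1 and 6.5.3). These do not adjust for prognosis.

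Several candidate covariates are already captured:

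- **KDIGO stage at randomization.** The outcome cannot be scored without it: "Progression of AKI is defined as the increase in KDIGO stage from the time of randomization to the present" (section 5.2.1).
- **Creatinine and the recommendation score.** Both are evaluated for every patient at screening. Whether an alert fires "will depend on the uplift score generated for each subject by the uplift algorithm" (section 6.3.3).
- **Age, surgical status and ICU status.** All are subgroup variables in section 6.4.1, the last defined as "Subjects in an ICU at the time of the alert".

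On power, section 6.4.2 assumes that the anti-recommended "arm will be 24%, and the rate in the" recommended arm 19.2%. It then says: "We are increasing this target sample size by 20% to 4,092 to account for contamination across the study arms". On monitoring, section 6.5.6 says: "The interim analyses will be performed at 25%, 50%, and 75% enrollment".

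**The concern.** The plan expects clinicians who see alerts on some patients to look harder for AKI in others, which would dilute the contrast between arms. Its stated protection against this is 682 extra patients (4,092 − 3,410). A second protection is available without recruiting anyone, namely adjusting for baseline variables that predict the composite. Section 6.5.1 rules this out and gives no reason. If the covariates are not fixed in advance, any later adjusted result will be post hoc. What is at stake is how much dilution the trial can absorb before power falls below the intended 90%.

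**Working it through.** **Inputs from the documents.** Event rates 24% and 19.2%, 90% power, 3,410 patients inflated to 4,092 (section 6.4.2). Looks at 25%, 50%, 75% and 100%; efficacy p < .0016, .0048, .014 and .044; futility p > .72 at 50% and > .22 at 75% (section 6.5.6).

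**Assumptions.** Two-sided p-values, 1:1 allocation, futility treated as binding, and a range of prognostic strength. The only c-statistic the plan mentions has no value and rates the ranking of alert recommendations, not prognosis.

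**Step 1: reproduce the sample size.** Per arm, n = [1.960·√(2 × .216 × .784) + 1.2816·√(.24 × .76 + .192 × .808)]² / .048² = 1,543, so 3,086 in total. The stated boundaries inflate this by 1.078, giving 3,325, or 3,414 with a continuity correction (3,168 × 1.078). The stated 3,410 is consistent with this, and 3,410 × 1.20 = 4,092.

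**Step 2: drift of the unadjusted test at N = 4,092 (2,046 per arm).**

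- 20% reduction: .048 / √[(.1824 + .1551)/2,046] = 3.737
- 16% reduction (24% vs 20.16%): .0384 / √[(.1824 + .1610)/2,046] = 2.964

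**Step 3: convert prognostic strength to precision.** I used a normally distributed linear predictor in a logistic model with mean risk .216, tuned to each c-statistic. R² = Var(p)/(.216 × .784). Adjustment divides the drift by √(1 − R²) and is worth 4,092 × [1/(1 − R²) − 1] patients (computed from unrounded R²).

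**Step 4: power under the stated boundaries.** These were computed by numerical integration. Simulation agrees to about 0.1 point.

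| Baseline c-statistic (assumed) | R² | Patients' worth | Power, 20% reduction | Power, 16% reduction | Smallest reduction with 90% power |
|---|---|---|---|---|---|
| none (as planned) | 0 | 0 | 95.0% | 81.4% | 18.1% |
| 0.60 | .0217 | 91 | 95.4% | 82.3% | 17.9% |
| 0.65 | .0498 | 214 | 95.8% | 83.4% | 17.6% |
| 0.70 | .0908 | 408 | 96.5% | 84.9% | 17.3% |
| 0.75 | .1459 | 699 | 97.3% | 87.1% | 16.8% |
| 0.80 | .2172 | 1,135 | 98.2% | 89.8% | 16.1% |

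The unadjusted floor, 18.08% before rounding, corresponds to a dilution of 1 − 18.08/20 = 9.6%. Only a c-statistic of about 0.75 or more matches the 682 patients added for contamination. If futility is ignored, power at a 16% reduction is about 83.5% unadjusted and 91.3% at c = 0.80, and the unadjusted floor is 17.6%.

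**Step 5: check against the actual comparator.** Under the null, 6,000 simulated trials per setting compared hospital-stratified Mantel-Haenszel with a standardized risk difference. Hospital was in both analyses and assumed unrelated to outcome. The variance ratios were 1.03, 1.07, 1.10, 1.19 and 1.30, against 1.02, 1.05, 1.10, 1.17 and 1.28 from the formula. The simulated predictors were slightly stronger than the tuned ones. Rejection at .044 was 4.4% to 4.7% adjusted and 4.1% to 4.6% for Mantel-Haenszel, so adjustment did not materially disturb the error rate.

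**The case against.** The strongest reply is that nothing is broken. The stratified test is valid, the choice is pre-specified in plain words, and the plan covers the contamination it budgets for. A 20% larger sample offsets a dilution of 1 − 1/√1.2 = 8.7%, leaving an 18.3% reduction. Power there is still about 90.7% unadjusted, and adjustment adds only 0.6, 1.3 and 2.4 points at c = 0.60, 0.65 and 0.70. The 16% scenario is a 20% dilution, more than twice that allowance, and no document supports it. The gain also spans a twelve-fold range.

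Most of this is correct and limits the point to efficiency. Three further cautions also stand:

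- Only prognostic strength beyond hospital counts, so the table leans towards upper bounds if hospital itself predicts outcome.
- The recommendation score was built to rank alert benefit and may predict the composite poorly.
- The ICU subgroup is defined at the time of the alert, which patients without an alert do not have. The covariate must therefore be ICU status at randomization.

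These points do not justify excluding adjustment. The plan itself expects dilution but gives no evidence that it will stay within 8.7%. The size of the gain can be measured, because the sponsor holds the earlier alert trial (6,030 patients, a composite of the same components) and already used it for modelling and event rates. Standardization keeps a marginal risk ratio, so the question the trial answers does not change.

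**Conclusion.** The point holds as a missed improvement that should be made. It is not an error in the planned test. With no dilution the benefit is small: power rises from about 95% to between 95.4% and 98.2%. Its value is as reserve, since the smallest relative reduction that keeps 90% power falls from 18.1% to between 17.9% and 16.1%. That the plan adjusts for hospital only, and that the covariates are available, is clear from the text. The size rests on the assumed c-statistics, two-sided testing, 1:1 allocation and binding futility. Confidence in the size is therefore medium.

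**What to change.** Before unblinding, pre-specify a covariate-adjusted marginal risk ratio and risk difference, from a logistic working model with standardization and robust standard errors. Covariates: hospital; recommendation stratum (score above 0.5 or not); KDIGO stage and creatinine at randomization; age; and ICU and surgical status at randomization. Fix their coding in advance. Estimating their prognostic strength in the earlier trial, restricted to the four participating hospitals, would replace the assumed range with a figure.

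- **If no interim look has been conducted:** make this the primary estimate and test at every look, with hospital-stratified Mantel-Haenszel as the sensitivity analysis.
- **If any look has been conducted:** keep Mantel-Haenszel as primary and report the adjusted estimate as a pre-specified supportive analysis. The power figures above then do not apply to the primary test.

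The documents do not say which case applies (version 3.0 is dated February 2025), so this must be confirmed first. The cost is modest extra programming and an amendment, with no new patients or data collection.

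### The plan allows three early efficacy stops but adapts only the p-value thresholds: after such a stop the ordinary pooled relative risk overstates the benefit on average, and no confidence interval is specified

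*Combined protocol and SAP*

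**What the plan says.** Section 6.5.6 sets looks at 25%, 50% and 75% enrollment. For the first: "At the first interim analysis, the trial will stop for efficacy if the p-value is < .0016". The efficacy thresholds at the second and third looks are .0048 and .014, with futility stops at p above .72 and .22. Section 6.4.1 gives the last threshold: "Final statistical significance will be based on a p-value of <0.044 to account for the interim analysis".

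On estimation, section 6.5.1 says: "The Mantel-Haenszel approach will be used to obtain the pooled relative risks across hospital strata", without covariate adjustment. Sections 6.4.1, 6.5.1 and 6.5.6 contain no bias-adjusted estimate, no repeated or stagewise interval, and no confidence level for the primary outcome. Nor does any other section.

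Section 6.4.2 plans on event rates of 24% (anti-recommended) and 19.2% (recommended), an RR of 0.80.

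**The concern.** A trial that stops at an early look has been selected for showing a large difference at that moment. The ordinary RR takes no account of this, so on average it lies too far from 1 after an early stop, most of all at the first look. The plan corrects the decision for repeated looks but not the number that will be reported.

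This matters because, at the planning rates, an early efficacy stop is the most likely ending. It matters more if the true effect is weaker than planned, which is plausible: the RR of 0.80 comes from ELAIA-1, whose data also trained and tuned the alert policy (sections 5.1 and 6.4.2), and the plan itself expects contamination to dilute the effect (sections 6.4.1 and 6.4.2). Since the interval is unspecified, it would be chosen after the result is known, and could disagree with the trial's own decision rule.

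**Working it through.** **Inputs.** From the plan: rates of 24% and 19.2%, total alpha 0.05, 90% power at 3,410, target 4,092 (6.4.2); looks and thresholds (6.5.6). Assumed, because not stated: 1:1 allocation between arms, two-sided tests, one stratum, outcomes complete at each look.

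**The plan's own sample size.** A fixed design with the pooled-variance formula gives, per arm, (1.960·√(2·0.216·0.784) + 1.282·√(0.24·0.76 + 0.192·0.808))² / 0.048² ≈ 1,543, or 3,086 in total. With the four looks and the printed efficacy and futility limits, 90% power needs about 3,330, and 3,410 gives 90.7%. So 3,410 is consistent with the sequential design, and 3,410 × 1.2 = 4,092.

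**Type I error.** The four efficacy thresholds together give 0.0498 two-sided without futility stops and 0.046 with them. The test is controlled.

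**What each look requires.** The printed p-values correspond to |z| of 3.156, 2.820, 2.457 and 2.014. At look 1 there are about 511.5 patients per arm. With 24% observed in the anti-recommended arm, z = (0.24 − p) / √(2·p̄(1 − p̄)/511.5), where p is the rate in the recommended arm and p̄ the mean of the two rates. This reaches 3.156 at p = 0.161, an RR of about 0.67. The corresponding limits at looks 2 to 4 are 0.787, 0.846 and 0.890. A look-1 stop therefore has to report a reduction of roughly a third, whatever the truth.

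**Simulation** (two binomial arms, N = 4,092, futility applied, 400,000 trials per scenario). The first three result columns concern early efficacy stops. Coverage is that of an ordinary 95% interval on the log RR.

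| True RR | Early efficacy stop | Mean RR reported | Coverage after such a stop | Coverage, all trials |
|---|---|---|---|---|
| 0.80 | 79% | 0.76 | 96% | 93% |
| 0.85 | 49% | 0.785 | 92% | 93% |
| 0.90 | 20% | 0.80 | 81% | 94% |

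By look, at true RR 0.80:

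| Look | Probability of efficacy stop | Mean RR reported | Coverage |
|---|---|---|---|
| 1 | 9.8% | 0.646 | 75% |
| 2 | 34% | 0.748 | 98% |
| 3 | 35% | 0.805 | nearly 100% |

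At true RR 0.90 the means at looks 1 to 3 are 0.665, 0.769 and 0.826.

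**Final look.** A final p between .044 and .05, where a 95% interval could exclude 1 although the trial misses its threshold, occurs in about 0.3% of trials at RR 0.80 and 1.6% at RR 0.90.

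**Effect of a repeated interval.** Its half-width is the look's critical value in place of 1.960, so the ratios are 3.156/1.960 = 1.61, 2.820/1.960 = 1.44, 2.457/1.960 = 1.25 and 2.014/1.960 = 1.03 on the log scale. Example at look 1 with observed RR 0.65: the standard error of log RR is √(0.76/(0.24·511.5) + 0.844/(0.156·511.5)) = 0.1295. The ordinary interval is 0.65·exp(±1.960·0.1295) = 0.504 to 0.838; the repeated interval is 0.65·exp(±3.156·0.1295) = 0.432 to 0.978. Over all trials repeated intervals cover 98–99% at true RRs of 0.80 to 0.90.

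**Effect of an adjusted estimate.** The Whitehead bias-adjusted estimate solves for the true RR at which the expected log RR equals the one observed. It moves observed RRs of 0.65, 0.75 and 0.81 at looks 1 to 3 to about 0.67, 0.77 and 0.83. The stagewise median-unbiased estimate gives 0.650, 0.754 and 0.817, so it leaves a look-1 result unchanged.

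**The case against.** The decision rule is sound, and neither sample size nor alpha needs to change on this ground. That stands.

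A reader might infer that the plan's 95% interval is too narrow. The documents do not support this: they state no interval, so the defect is that it is missing. Nor would an ordinary 95% interval be generally too narrow. Coverage over all trials is 93–95%, and it is 96% after early efficacy stops at the planning effect. At look 1 the stagewise interval equals the ordinary one (0.504 to 0.838 in the example), so the shortfall there comes mainly from a shifted estimate.

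A reader might also infer that every early stop exaggerates. At true RR 0.80, look 3 is the most likely stopping point and its mean is 0.805, which is no overstatement. Over all trials at true RR 0.90 the geometric mean RR is 0.900. Coverage after a look-1 stop at RR 0.90 is 0%, but such stops happen in only 1.2% of trials.

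Finally, adjusted estimates move little, section 3.2.2 ties deployment to no particular effect size, and the RR contrasts recommended with anti-recommended alerting, so it is not the effect of deployment against usual care. All true. These points limit the size of the issue. They do not remove the average overstatement after an early stop or the absence of an interval rule.

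**Conclusion.** The point holds as a gap in estimation and reporting. Followed as written, the plan gives a headline RR that is too favourable on average after an early efficacy stop: 0.76 against a true 0.80, and 0.80 against a true 0.90. The excess is large at look 1, modest at look 2, and absent at look 3 if the planning effect is true. An interval for the primary outcome is unspecified. If an ordinary 95% interval were used by default, its overall coverage would fall short by at most about 2 points, with a marked loss after early stops only when the true effect is weaker than planned (81% at RR 0.90).

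These figures rest on the assumptions listed with the inputs, on the 24% rate, and on three interim looks as in section 6.5.6. The true RRs of 0.85 and 0.90 are illustrative, not values from the plan.

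**What to change.** In sections 6.5.1 and 6.5.6, before any unblinded result is seen:

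- Report the Mantel-Haenszel RR with a repeated confidence interval at the level matching the threshold of the look at which the trial ends: 99.84%, 99.52% or 98.6% at looks 1 to 3, and 95.6% at the final look. Interval and decision then follow the same threshold.
- If the trial stops early for efficacy, report beside it one named bias-adjusted estimate, for example the Whitehead bias-adjusted maximum likelihood estimate. It reduces bias averaged over all possible endings. It does not fully undo the exaggeration given a look-1 stop, and the report should say so.

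The cost is SAP wording and a few lines of code. The intervals are about 61%, 44%, 25% and 3% wider at looks 1 to 4 and are conservative.
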